7 DATA ANALYSIS SUMMARY

The primary objective of this study is to determine the safety in phase I part and efficacy in phase II part of VENETOCLAX administered with AZA/DLI in patients with myeloid neoplasms in relapse after allo hematopoietic stem cell transplantation. Summary statistics (median and range) will be provided. Adverse experiences and lab assessments will be summarized.

8 VISIT STUDY PROCEDURES

8.1 Screening Period

The investigator is responsible for keeping a record of all subjects who sign an Informed Consent Form for entry into the study. All subjects will be screened for eligibility. Screening procedures must take place within 2 weeks prior to initiation of therapy. A maximum of 48 subjects will be included.

Screening visit can be accomplished over one or multiple visits over a 2-week period (14 days), unless specifically noted otherwise (ie, bone marrow sample collection). Protocol specific tests or procedures not considered standard of care can only be done after the patient has signed the Informed Consent document. See the Flow Chart for a complete list of assessments and procedures to be collected during the screening visit.

A patient who signs an ICF but fails to begin treatment for any reason will be considered as a screen failure. The reason for not beginning treatment and the demographic information should be entered in the screening eCRF page. Information on death or withdrawal of consent, if applicable, must also be completed. No other data will be entered into eCRF for patients who are screen failures, unless the patient experienced a serious or nonserious adverse events considered by the investigator to be causally related to the study-required procedures.

8.2 Study Period

See the visit schedule (Appendix 1) for a detailed list of the assessments and procedures to be collected. Study entry is defined as when the patient is enrolled.

8.3 Treatment

See the visit schedule (Appendix 1) for a detailed list of the assessments and procedures to be collected.

8.4 Before Each Course

See the visit schedule (Appendix 1) for a detailed list of the assessments and procedures to be collected.

8.5 Assessment at Evaluation

See the visit schedule (Appendix 1) for a detailed list of the assessments and procedures to be collected.

8.6 End-of-Study (EOS) Visits

See the visit schedule (Appendix 1) for a detailed list of the assessments and procedures to be collected.

8.7 Follow-Up

Follow-up after treatment discontinuation for all patients.

Patients will be followed at 3 months and 6 months after treatment discontinuation. Date of death or last follow-up, disease status, and ongoing hematological treatments will be collected.

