Each dose of venetoclax should be taken with approximately 240 mL of water within 30 minutes after the completion of a meal (preferably breakfast). Exceptions may apply if food is not allowed for medical procedures. Tablets must be swallowed whole and must not be broken, chewed, or crushed. The dose should be administered at the same time each day.

On days of concomitant administration of azacitidine, venetoclax should be given prior to azacitidine.

If vomiting occurs after taking venetoclax, do not take any additional dose that day. Take the next dose at the usual time the next day. A missed dose of venetoclax should be taken with food and water within 8 hours of the missed dose. After 8 hours, the missed dose should not be taken. The next dose of venetoclax will be the regularly scheduled dose.

Azacitidine

Azacitidine will be administered at the dose of 75 mg/m²/day for 5 days for each cycle or 50 mg/m²/day for 5 days each cycle if relapse occurred less than 4 months after allo SCT and should be prepared according to the information provided in the Summary of Product Characteristics (SmPC) and will be administered, by IV infusion or SC injection.

BIOLOGICAL STUDIES

Mutational analysis (Hematology Laboratory, CHRU Lille)

Immunologic analysis (Immunology Laboratory, Saint Louis hospital, Paris and INSERM U1065, Mediterranean center of molecular medicine, Nice)

At screening and during follow up (after 4 and 8 cycles and at the end of the study) presence of all identified mutations will be investigated with the same technique. All mutation-specific primers and probes will be designed by Biorad (Hercules, CA).

OVERALL DURATION OF THE STUDY: 42 MONTHS

Recruitment months: 24 months

Duration of Treatment: 12 months

Follow-up for all patients: 6 months

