3	100 mg*	200 mg*	400 mg*

*VENETOCLAX will be given once daily orally.

**Therapy with CYP3A inhibitor are not allowed during the ramp up.

DLI will be infused every two cycles (C2, C4, C6, C8) at day 15 in absence of GVHD as follows, and at least 8 weeks after immunosuppressive therapy discontinuation. If the chimerism in > 90% recipient, DLI will not be performed.

	DLI dosage
Sibling-Id or Unrelated Donor-Id 10/10	0.5 x 10 ⁷ CD3/kg 1 x 10 ⁷ CD3/kg 0.5 x 10 ⁸ CD3/kg 1 x 10 ⁸ CD3/kg
Unrelated Donor-Id 9/10	1 x 10 ⁶ CD3/kg 5 x 10 ⁶ CD3/kg 1 x 10 ⁷ CD3/kg 0.5 x 10 ⁸ CD3/kg

Patients with Complete Remission (CR), Partial Remission (PR), marrow CR or Hematological Improvement (HI) after 8 Cycles of therapy (IWG 2006 criteria or Cheson et al. criteria for AML) continue on protocol with VENETOCLAX + AZA until 12 cycles maximum then AZA alone. Patients with no response (NR) to treatment will be withdrawn from the protocol after the last treatment Cycle.

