6.8 Patient Withdrawal Criteria

Patients are free to discontinue their participation in the study at any time and without prejudice to further treatment. The Investigator must withdraw any patient from the study if that patient requests to be withdrawn. The patient's participation in this study will be discontinued due to the following reasons:

- Death
- Withdrawal of the patient's consent
- Occurrence of AEs for which permanent discontinuation of study medication is desired by the patient or considered necessary by the Investigator or by the Sponsor
- Use of illicit drugs or other substances that may, in the opinion of the Investigator, have a reasonable chance of contributing to toxicity or otherwise skewing results
- Development of an intercurrent illness or situation which would, in the judgment of the Investigator or the Sponsor, affect assessments of clinical status and study endpoints to a significant degree
- Development of a second cancer that requires treatment
- If, in the Investigator's opinion, continuation in the study would be detrimental to the patient's well-being
- Lack of patient compliance
- Serious protocol deviation that affects patient safety and accuracy and/or validity of data
- Patient is lost to follow-up
- Inability to continue in the study for any reason
- Intake of disallowed medication
 - Initiation of any experimental therapy in any period of the study until study treatment failure has been established.
 - Initiation of any anti MDS or AML therapy until study treatment failure has been established.
- Pregnancy

- Study terminated by the Sponsor

If a patient is discontinued from the study for any reason, the date of discontinuation and the reason for the discontinuation must be recorded and all evaluations specified in the EOS visit (**See the visit schedule (Appendix 1)**) must be completed. In cases of discontinuation due to an AE (including death) or pregnancy, the relevant pages of the (electronic Case Report Form) eCRF must be completed. If possible, all patients who discontinue study medication due to an AE should be followed until the medical condition returns to baseline or is considered stable or chronic.

Patients unwilling to be treated with all of the courses they are eligible for, will not be withdrawn from the study if they complete at least one treatment course, and will be followed to the full extent of the study period.

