Overall survival (OS) will be defined as the number of days from the date of the first dose of study drug to the date of death. Overall survival will be analyzed by Kaplan-Meier methodology. Median OS will be calculated and 95% confidence interval for median OS will be presented. Data from subjects that are alive at the time of analysis will be censored at the date of last study visit or the last known date the subject was alive, whichever is later.

Progression-Free Survival

Progression-free survival (PFS) will be defined as the number of days from the date of the first dose of study drug to the date of earliest disease progression or death due to disease progression or febrile neutropenia. Progression-free survival will be analyzed by Kaplan-Meier methodology. Median PFS will be calculated and 95% confidence interval for median PFS will be presented. All events of disease progression will be included regardless whether the event occurred while the subject was taking the study drug or had previously discontinued the study drug. Refer to Appendix 11 and 12 for the definition of disease progression. If the subject has not experienced disease progression or death, the subject's data will be censored at the date of last disease assessment. Data for subjects without any disease assessments performed after the first dose of study drug will be censored at the time of the first dose of study drug.

Event-Free Survival

Event-free survival (EFS) will be defined as the number of days from the date of the first dose of study drug to the date of earliest disease progression or death of any cause.

Event-free survival will be analyzed by Kaplan-Meier methodology. Median EFS will be calculated and 95% confidence interval for median EFS will be presented. All events of disease progression will be included regardless whether the event occurred while the subject was taking the study drug or had previously

discontinued the study drug. If the subject has not experienced disease progression or death, the subject's data will be censored at the date of last disease assessment. Data for subjects without any disease assessments performed after the first dose of study drug will be censored at the time of the first dose of study drug.

Safety assessments

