13.13 PREMATURE TREATMENT DISCONTINUATION (Discontinuation of Individual Subjects)

Treatment will continue until the occurrence of any of the following events:

- No response after 8 cycles of therapy
- Major violation of the study protocol (violations that affect the right and safety of patients and the integrity of collected data)

- Unacceptable AE or failure to tolerate study therapy
- All grade 4 toxicities
- Persistent myelosuppression and/or cardiac toxicity
- Disease progression
- Withdrawal of consent
- Lost to follow up
- Death
- Suspected pregnancy
- Administrative decision by the investigator or the sponsor
- If the patient manifests exclusion criteria during the trial
- Subject noncompliance (deliberate protocol violations)
- A subject requires the use of a proscribed medication; the subject will need to be discontinued from treatment and end of treatment and end of study visits performed.

Where possible, patients who have discontinued their treatment prematurely will receive the same follow-up as other patients.

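### Scheduled survival follow-up ends 6 months after each patient's own treatment stop, so OS censoring depends on outcome and OS beyond about month 12 is expected to be biased upward

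*Protocol*

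**What the plan says.** Protocol section 8.7 sets the only contacts after treatment: "Patients will be followed at 3 months and 6 months after treatment discontinuation". What is gathered then is also stated: "Date of death or last follow-up, disease status, and ongoing hematological treatments will be collected". The synopsis gives the study timeline as 24 months of recruitment, 12 of treatment and a closing item, "Follow-up for all patients: 6 months", for a total of 42 months.

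When treatment stops depends on how the patient does. Under section 6.1, patients without a response stop, and responders go on with venetoclax plus azacitidine to at most 12 cycles and then azacitidine alone, with no stated end. Section 13.13 lists no response after 8 cycles, progression and toxicity among the reasons for stopping. It adds: "Where possible, patients who have discontinued their treatment prematurely will receive the same follow-up as other patients".

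Section 10.2 defines OS from first dose to death and analyses it by Kaplan-Meier, with the median and its 95% confidence interval. Patients alive are "censored at the date of last study visit or the last known date the subject was alive, whichever is later".

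Two passages describe leaving the study rather than only stopping treatment. Section 6.1: "Patients with no response (NR) to treatment will be withdrawn from the protocol after the last treatment Cycle". Section 6.8 lists, among reasons for ending participation, "Occurrence of AEs for which permanent discontinuation of study medication is desired by the patient". Section 6.8 also has one exception: patients who decline further courses after completing at least one are followed for the whole study period.

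**The concern.** Kaplan-Meier assumes that a patient censored at a given time has the same future risk of death as the patients still under observation. Here the censoring time is tied to the date of treatment stop, which is itself tied to non-response, progression or toxicity. The patients expected to do worst have the shortest scheduled observation, and the later part of the curve rests increasingly on responders. The expected effect is an OS curve that lies too high once follow-up of the non-responders has run out.

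A later analysis plan cannot repair this, because vital status that was never collected cannot be analysed. In a single-arm trial, readers will set the OS curve beside earlier azacitidine/DLI series, even though the protocol plans no such comparison.

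**Working it through.** **1. Timeline from the protocol.** 24 + 12 + 6 = 42 months, as the synopsis states. The last patient included at month 24 therefore has 42 − 24 = 18 months before study end.

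**2. Scheduled follow-up per patient** (cycles of 28 days, 30.44 days per month, plus 6 months from section 8.7):

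| Treatment stop | Time of stop | Last scheduled contact |
|---|---|---|
| After cycle 2 | 2 × 28 / 30.44 = 1.8 months | 7.8 months |
| After cycle 8, no response | 8 × 28 / 30.44 = 7.4 months | 13.4 months |
| After cycle 12, responder | 12 × 28 / 30.44 = 11.0 months | 17.0 months |

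Responders who stay on azacitidine alone are followed longer, and responders who stop early for progression or toxicity are followed for less. If every cycle were delayed to 42 days, a non-responder would stop at 8 × 42 / 30.44 = 11.0 months.

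**3. Size of the bias.** The protocol gives no survival figures, so these inputs are assumptions:
- response 30% or 50% (the two rates in section 3);
- exponential survival, with median 20 or 30 months in responders and 5 or 8 months in non-responders;
- treatment stop uniform over 1 to 7.4 months in non-responders and 11 to 24 months in responders;
- uniform entry over 24 months and study end at month 42.

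True OS follows directly: S(t) = p·2^(−t/m_R) + (1 − p)·2^(−t/m_N), where p is the response rate and m_R and m_N are the medians in responders and non-responders. For p = 0.5, medians 30 and 8, t = 18: 0.5 × 0.660 + 0.5 × 0.210 = 0.435. OS under the planned follow-up was simulated (400,000 patients per scenario), censoring at the earlier of treatment stop + 6 months and month 42. The comparison is Kaplan-Meier with everyone followed to month 42.

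| Response | Median R / NR (months) | 18-month OS, planned | 18-month OS, common cut-off | Gap (points) | Median gap (months) |
|---|---|---|---|---|---|
| 30% | 20 / 5 | 0.284 | 0.219 | 6.5 | 0.0 |
| 30% | 30 / 5 | 0.332 | 0.255 | 7.7 | 0.0 |
| 30% | 20 / 8 | 0.372 | 0.308 | 6.4 | 0.2 |
| 30% | 30 / 8 | 0.426 | 0.344 | 8.2 | 0.6 |
| 50% | 20 / 5 | 0.358 | 0.308 | 5.0 | 0.1 |
| 50% | 30 / 5 | 0.430 | 0.371 | 5.9 | 0.8 |
| 50% | 20 / 8 | 0.421 | 0.372 | 4.9 | 0.9 |
| 50% | 30 / 8 | 0.499 | 0.436 | 6.3 | 3.4 (17.9 vs 14.5) |

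At 12 months the gap is about 1.5 to 2.5 points. The common cut-off reproduces the true curve up to simulation error.

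**4. Sensitivity to the model.** A second model lets death follow progression. It assumes non-responder median time to progression of 3 months, responder median of 12 months from cycle 4, median survival after progression of 2 to 12 months, and responders kept on azacitidine. The gap is 0 at 6 months, +2 to +5 points at 12 months and +6 to +14 at 18 months. With strong variation between patients in survival after progression (gamma frailty, variance 2), it falls to about +1 at 12 months and +4 to +5 at 18 months. The median gap in this model depends heavily on survival after progression. It is 0.1 to 0.4 months if that is 2 months. With 50% response it is 3.1 months (16.8 vs 13.7) if that is 4 months, and 7.1 months (23.6 vs 16.5) if it is 6 months. The direction was upward in every scenario of both models, but the documents do not fix the size.

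**5. EFS and PFS.** A patient who stops for progression already has the event, so only those who stop progression-free can be affected. With the progression times of step 4, 30% or 50% response and 15% random stops for adverse events, the EFS gap was 0.0 points at 6 and 12 months, about +1 point at 18 months, and 0 for the median. Section 9.1 also restricts PFS to responders, which under that definition leaves non-responders out altogether.

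**The case against.** The strongest defence is that the synopsis can be read as a common closing period of 6 months after the last patient's treatment. On that reading everyone is followed to month 42 and the problem disappears. Section 8.7, however, counts from each patient's own discontinuation, so the two statements need to be reconciled. The OS censoring rule also accepts a later last-known-alive date, but nothing schedules that contact, and chance updates would not remove the dependence on outcome.

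The withdrawal wording in sections 6.1 and 6.8 can be read as going off protocol treatment, since section 8.7 is addressed to all patients. That is fair. It is an ambiguity to clear up, not proof that these patients are lost at once.

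The bias could also shrink or reverse if patients alive 6 months after stopping had a lower hazard than those still on treatment, for example after successful later therapy. The documents do not suggest this, but they do not exclude it.

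Several stronger readings are tempting and are not supported:
- That EFS and PFS are biased in the same way: they are not, for the reason in step 5.
- That median OS is read mainly from responders: in seven of the eight main scenarios the median moves by less than 1 month. The median is the OS summary that section 10.2 names, and it names no 18-month rate.
- That every responder is observed for at least 17 months: section 13.13 also stops responders for progression or toxicity, and they are then followed for less.
- That a planned comparison with azacitidine/DLI survival would be distorted: the 30% versus 50% hypothesis and the decision rule concern response only.

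**Conclusion.** The point holds for OS. As written, section 8.7 makes scheduled follow-up depend on outcome, and the Kaplan-Meier OS estimate after about month 12 is expected to be too high. The direction follows from the protocol's own rules plus the ordinary expectation that patients who have stopped for failure or toxicity die sooner. The size rests on assumed survival: about 5 to 8 points at 18 months, about 1.5 to 2.5 points at 12 months, and a median gap below 1 month in most scenarios and 3.4 months in one. The second model shows that the gap could be larger if survival after progression is longer.

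The consequence is limited. OS is a descriptive secondary endpoint, and the primary response analysis, the sample size and the go/no-go rule do not depend on it. EFS and PFS are touched only slightly, through patients who stop without progression. The change is still worth making because it is cheap and the missing data could not be recovered later.

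**What to change.** In section 8.7, collect vital status (date of death or date last known alive, by chart or telephone) for every treated patient, whatever the date or reason of treatment stop, up to one common calendar cut-off at study end (month 42). In section 10.2, censor OS at that cut-off.

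Reconcile section 8.7 with the 6-month follow-up line in the synopsis. Reword the withdrawal passages in sections 6.1 and 6.8 so that stopping treatment does not end survival follow-up, except when consent is withdrawn. Nothing in the treatment rules needs to change for this.

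The cost is a small number of extra status checks on patients already off treatment. The stated 42 months already give at least 18 months after the last inclusion, so the study is not lengthened. Regular marrow-based progression assessment to month 42 is not needed to correct OS and would not be cheap.

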8.8 Early Discontinuation Study Visit

If a patient discontinues prematurely from the study, the same procedures planned for the EOS visit will be performed. Other procedures and evaluations will be completed as deemed necessary by the Investigator. If an early discontinued patient refuses to participate in the scheduled EOS visit, and an AE that started during or within 30 days of the last study drug dose and assessed as possibly or probably related to study drug was present at last visit, the patient will be followed until the medical condition returns to baseline or is considered stable or chronic.

8.9 Unscheduled Visit

An unscheduled visit may be performed at any time during the study at the patient's request or as deemed necessary by the Investigator. The date and reason for the unscheduled visit will be recorded. AE monitoring and concomitant medication recording will be performed by the Investigator. Other procedures and evaluations will be completed as deemed necessary by the Investigator and may include (but not limited to) laboratory tests, BM evaluations, ECG, vital signs, and physical examination.

8.10 Bone Marrow Aspirate

Please see the visit schedule (Appendix 1) specific assessment timepoints for Bone Marrow Aspirate collection. For MDS patients' CR or PR need to be confirmed at least 28 days after the BM evaluation by assessing the stability of improved counts on PB according to the IWG criteria; the need for an additional marrow confirmatory specimen is not required.

The importance of timely and complete disease assessments (including BM and PB assessments) at screening and during the study, whenever clinically indicated, cannot be understated. Failure to perform any of the required disease assessments will result in the inability to determine disease status for that time point and have the potential to weaken the conclusions of this study.

8.11 Safety Assessments

Safety assessments will be based on changes from baseline of AEs reported by the patients or observed by the Investigator, concomitant medication and blood product use, treatment discontinuation due to AEs, vital signs, ECG, physical examination, laboratory assessments (hematology, blood chemistry), and evaluation of the performance status by the ECOG.

AEs and SAEs will be graded according to the CTCAE, version 5. All AEs (serious and non-serious) occurring between Study Day 1 and 30 days following the last dose of study treatment of each course will be documented in the trial subject's medical records. The following AEs will additionally be documented in the eCRF if:

- Serious (SAE) as defined in 13.2, whether or not related to study drug,
- Related to study drug, regardless of grade and clinical significance,
- Unrelated to study drug but grade ≥ 3 and clinically significant.

AEs and SAEs occurring after 30 days of the last study treatment dose in each course, should only be recorded if considered at least possibly related to study treatment by the local investigator. SAEs and Grade 3 or higher AEs that are ongoing at the end of this period (30 days from last study treatment administration) will be followed until each event is resolved or is assessed as chronic. Serious and nonserious adverse events occurring after the study-specific informed consent is signed but prior to Study Day 1 will be collected only if they are considered by the investigator to be causally related to the study-required procedures.

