5.2 Secondary endpoints

- ✓ Toxicity as measured by NCI CTCAE 5.0
- ✓ Acute and chronic GVHD rate
- ✓ Duration of response (DOR)
- ✓ Overall survival (OS)
- ✓ Progression-free survival (PFS)
- ✓ Event-free survival (EFS)

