9.2 Safety and Tolerability Outcome Measures

Safety outcomes:

1. AEs analyzed by frequency, NCI-CTC grade, and causality
2. Serious Adverse Events (SAEs) and events of special interest (injection site reactions, infections, new malignancy, tumor lysis syndrome)
3. Withdrawal rates, days and reasons for withdrawal
4. Dose modifications and treatment delays
5. Serum chemistry and hematology laboratory values; change from baseline and worst NCI-CTC grade

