12.2 Identity of Investigational Products

Information about the venetoclax and azacitidine formulations to be used in this study is presented below:

Identity of Investigational Products

Study Drug	Formulation	Route of Administration
Venetoclax	10 mg tablet	Oral
Venetoclax	50 mg tablet	Oral
Venetoclax	100mg tablet	Oral

Packaging and Labeling

Venetoclax tablets will be packaged in bottles or blister cards to accommodate the study design. Each bottle or blister card will be labeled per local regulatory requirements. Each tablet contains 10 mg, 50 mg, or 100 mg of venetoclax.

Storage and Disposition of Study Drugs

Venetoclax must be stored at 15° to 25°C (59° to 77°F). The investigational products are for investigational use only and are to be used only within the context of this study. The study drug supplied for this study must be maintained under adequate security and stored under the conditions specified on the label until dispensed for subject use or returned to sponsor.

For more information about Venetoclax, please refer to the IB

Identity of Non-Investigational Products

Study Drug	Formulation	Route of Administration
Azacitidine	100 mg lyophilized powder for injection	SC or IV ^a

a. According to local regulations.

For more information about azacitidine, please refer to SmPC

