The investigator will document, according to his/her opinion, the relationship of the AE to the study treatment using the criteria outlined in visit schedule (Appendix 1). The nature of each event, start and end date, action taken in response to the event, outcome, NCI CTCAE toxicity grade, relationship to study treatment, and whether the event is serious, should be established and recorded on the AE eCRF. All entries must be clearly documented in the source documents. AEs documented in the eCRF without a stop date should be reviewed at subsequent visits. Documentation on AEs should be updated as necessary. In case of worsening of an AE (i.e. AE grade increase) the event should be captured with the maximal severity observed providing that the AE is ongoing while the AE grade increased.

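### The GVHD rate is a secondary endpoint, but the protocol's conflicting recording rules and its follow-up data list put it at risk of under-ascertainment

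*Protocol*

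**What the plan says.** **Endpoint.** Section 5.2 and the synopsis list "Acute and chronic GVHD rate" among the secondary endpoints. GVHD does not appear among the outcome measures of section 9 or the analyses of section 10. Section 9.2 names "events of special interest (injection site reactions, infections, new malignancy, tumor lysis syndrome" and stops there.

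**Entry in the eCRF.** Section 8.11 says that adverse events from Study Day 1 to "30 days following the last dose of study treatment of each course will be documented in the trial subject's medical records". It then limits eCRF entry to three groups: serious events; events "Related to study drug, regardless of grade and clinical significance"; and events "Unrelated to study drug but grade ≥ 3 and clinically significant". Section 13.1, on the same subject, lists grade, relationship and "whether the event is serious, should be established and recorded on the AE eCRF", with no filter on grade or causality.

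**What counts as study drug or study treatment.** The synopsis names venetoclax as the study drug. Section 12.2 opens with "Information about the venetoclax and azacitidine formulations to be used in this study is presented below", then lists venetoclax as investigational and azacitidine as non-investigational. Section 12.1 covers the same two drugs. Note b of Appendix 1 defines a full cycle by azacitidine and venetoclax. DLI is in none of these. Section 6.1, however, describes the regimen as venetoclax, azacitidine and DLI together.

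**After the 30-day window.** Sections 8.11 and 13.1 keep a later event only if the local investigator considers it at least possibly related to study treatment. Patients are seen 3 and 6 months after stopping treatment, and for those visits section 8.7 says "Date of death or last follow-up, disease status, and ongoing hematological treatments will be collected".

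**The concern.** GVHD is the characteristic harm of donor lymphocytes. Section 2(d) puts forward a low GVHD rate as part of the rationale, and section 2(a) gives 37% acute and 17% chronic GVHD for azacitidine plus DLI, which a reader will use as the yardstick. If mild-to-moderate cases blamed on DLI, or cases that appear late, are not recorded, the numerator falls and the denominator stays the same. The error runs one way, towards the hoped-for result. An analysis plan cannot repair it: data that were never collected cannot be analysed, and section 10.2 says that missing values are not imputed. With about 20 sites, two conflicting entry rules also invite sites to record differently.

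**Working it through.** No design figure is attached to this endpoint, so there is nothing of the plan's own to reproduce beyond the background rates. The check compares the recording rules, works out the window after the last DLI, and illustrates sensitivity.

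**1. Background rates (section 2(a)).** 22 patients are given as 73%, so the denominator is about 22/0.73 = 30.1, i.e. 30. Then 11/30 = 36.7% and 5/30 = 16.7%, which agree with the stated 37% and 17%.

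**2. Which GVHD cases inside the window reach the eCRF?**

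| GVHD case | Section 8.11 | Section 13.1 |
|---|---|---|
| Serious, any attribution | entered | entered |
| Any grade, judged related to study drug | entered | entered |
| Not serious, judged unrelated, grade 3 or more and clinically significant | entered | entered |
| Not serious, judged unrelated, grade 1-2 | **not entered** | entered |

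The fourth row is where the sections disagree. A case attributed only to DLI falls into it if DLI is not a study drug, which is how the synopsis, sections 12.1-12.2 and Appendix 1 read.

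**3. Window after the last DLI.** Section 6.1 schedules DLI on day 15 of cycles 2, 4, 6 and 8, and venetoclax on days 1-14. For a patient who stops after cycle 8:
- last venetoclax dose on day 14, plus 30 days = day 44; 44 - 15 = **29 days** after the DLI;
- if the DLI itself counts as the last dose, 15 + 30 = day 45; 45 - 15 = **30 days**.

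The end-of-study visit is due within 30 days of stopping study drug (Appendix 1, note c). After that, recording depends on the causality clause. The 6-month visit comes roughly five months after the window closes (6 months less 30 days), and GVHD is not on its data list.

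**4. Sensitivity to an assumed loss.** Let f be the share of GVHD patients not entered. The documents give no value for f; those below are assumptions. Reported rate = true rate × (1 - f).

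| True rate (assumed equal to background) | f = 20% | f = 40% | f = 60% |
|---|---|---|---|
| 37% acute | 29.6% | 22.2% | 14.8% |
| 17% chronic | 13.6% | 10.2% | 6.8% |

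In counts for acute GVHD, with exact (Clopper-Pearson) 95% intervals:
- N = 30: 0.37 × 30 = 11.1, about 11 (19.9-56.1%). At f = 40%, 6.7, about 7 (9.9-42.3%).
- N = 48: 0.37 × 48 = 17.8, about 18 (24.0-52.6%). At f = 40%, 10.7, about 11 (12.0-37.3%).

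The intervals overlap widely, so a loss of this order could not be recognised from the reported result.

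**The case against.** A reader might infer that the protocol certainly drops these cases and that the reported rate will be too low. The text does not go that far.

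- **Section 13.1** records events on the eCRF without a filter, and section 10.2 plans incidence tables for all adverse events. This stands. It makes the matter a contradiction between sections, not a settled exclusion.
- **Attribution.** Section 13.4 treats an event as a reasonable possibility when a link with study treatment cannot be ruled out. DLI follows venetoclax by one day, so an investigator may seldom rule out a contribution, and related events enter at every grade. This narrows the gap but does not close it: the same table lists explanation by other therapy given to the patient among the grounds for judging an event unrelated, although two grounds are needed.
- **Late chronic GVHD** is not excluded outright, since possibly related events are kept. This stands, but it depends on whether DLI is study treatment, which is left open.
- **The window** of 29-30 days applies to patients stopping after cycle 8. Responders may continue, and the window then moves on with each course. This stands.
- **The eCRF is not shown**, so a dedicated GVHD page cannot be ruled out. Absence from Appendix 1 is weak evidence, because DLI has no row there either. GVHD status must be known before each DLI, but no text asks for it to be recorded as an outcome.
- **Weight.** The endpoint is descriptive, with no test or formal comparison planned. This stands and limits the severity.

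**Conclusion.** The concern holds as a risk of under-ascertainment. Three things support it: sections 8.11 and 13.1 conflict on whether non-serious grade 1-2 GVHD attributed only to DLI is entered; the protocol does not settle whether DLI is study treatment, on which late capture depends; and section 8.7 does not list GVHD at visits that already exist. The direction is certain, because a patient whose GVHD is not recorded can only lower the rate. The size is not: it depends on the unknown f, and the table above is illustration, not estimate. Serious cases, clinically significant cases of grade 3 or more, and cases of any grade judged related to study drug are captured within the window under either section. This should be fixed, at a level fitting a descriptive secondary safety endpoint.

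**What to change.** 1. Reconcile section 8.11 with section 13.1, so that one rule governs eCRF entry.
2. State whether DLI counts as study treatment, both for the causality judgement and for the 30-day window.
3. Add to section 8.11 that any acute or chronic GVHD, whatever its grade, seriousness or attribution, is recorded in the eCRF from Study Day 1 to the 6-month follow-up, with onset date, type (acute or chronic) and maximum grade.
4. Add GVHD status to the data collected at 3 and 6 months in section 8.7.

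The cost is about one eCRF page and a few lines of protocol. No visit or procedure is added, because physical examinations and follow-up contacts are already scheduled and GVHD must already be judged before each DLI. Treatment rules are untouched. The price to the sponsor is a GVHD rate that may look less favourable.
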